#### 6.3 Safety Evaluation

Subject safety will be monitored by tracking AE's. See Section 8.1 for details.

## 7 STATISTICAL CONSIDERATIONS

### 7.1 **Primary Endpoints**

We hypothesize that neurocognitive function in concussed subjects will initially worsen and then improve in a non-linear fashion over the course of the study, and that, compared to the placebo group, one or more of the BCAA dose level groups will show a reduced nadir in cognitive performance and/or a more rapid recovery. Currently, the time course of the worsening and improvement of neurocognitive function after concussion is not well understood. Thus, part of our study will aim to identify times when maximal differences between groups may be observed. The primary analysis in this exploratory study will consider three key time periods, Days 3-6, 7-10 and 11-14 when we expect differences in processing speed between the BCAA-treated groups and placebo to be largest.

### 7.2 Secondary Endpoints

- Repeated measurements of neurocognitive functioning (CCAT test of attention, learning, and working memory) sampled over a period of 21 days.
- Clinical symptoms.
- Time to return to school/work, and sports participation.
- Tolerability of BCAA's based on AE's.
- Compliance.
- Safety and incidence of AE's and serious adverse events (SAE's).

## 7.3 Statistical Methods

## 7.3.1 Baseline Data

The characteristics of the dose and placebo groups will be described using standard statistics (e.g. means, medians, standard deviations, or proportions). For all analyses, high dose group will continue to be evaluated together, despite slight change in concentration. Subgroup analysis will be done to evaluate any differences in those subjects who received the full 60 g/d dosing before this dose was decreased, versus the current 54 g/d dosing. Graphical procedures will be used to assess distributional assumptions and particularly the assumption of normality of outcome.

## 7.3.2 Primary Efficacy Analysis

The primary intent to treat analysis will include all subjects who enroll and contribute at least 10 days of data to the study. The mean trajectory in decline and recovery in processing speed is unknown. Thus the primary analysis will aim to determine whether there are differences in processing speed between the BCAA dose groups and placebo, and if so, at what time periods the differences are most pronounced. The primary analysis will focus on results for the first 10 days of the study when we anticipate that the majority of subjects will be highly compliant. We will model processing speed as a function of dose and day of study and will allow differences between dose groups to vary as a function of time through a series of interaction terms. To ensure that the number of interaction terms does not become too large, we will consider groups of two to four time points, looking specifically at whether

04/06/2018 V 0.16

there are differences between any of the dose groups and placebo at Days 1-2, 3-6, 7-10, 11-14, 15-18, 19-21. The primary analysis will consider three key time periods, Days 3-6, 7-10 and 11-14 when we expect differences in processing speed between the BCAA-treated groups and placebo to be largest. Since processing speed differs with age, the model will be adjusted for age to account for any imbalances in age between dose groups. A mixed effects model will be used to account for correlations between repeated measurements on individual subjects. Likelihood ratio tests will be employed to specifically test whether there are differences in mean processing speed between placebo and any of the BCAA doses at the three key time periods. These three global tests will be conducted at a family-wise error rate of 0.05, using a Bonferroni correction to account for the three individual global tests. If statistical significance is achieved for the global test, we will then compare individual dose levels to placebo within time periods, again using a correction for four multiple tests per key time period.

We note that with five treatment groups and 21 time points, there are a very large number of possible hypothesis tests that can be carried out with these data. If all of these tests were carried out without adjusting for multiple comparisons, we would undoubtedly find spurious associations. On the other hand, adjusting for large numbers of multiple comparisons substantially reduces the statistical power of a study. By focusing our testing for the primary efficacy analysis on three key periods where we adjust for a limited number of tests, we balance the need for a rigorous statistical testing procedure with a need to maintain statistical power.

An analysis of the Day 1-2, 15-18 and 19-21 data will follow the same format, but will be considered secondary and will not be formally corrected for multiple testing. In addition to hypothesis testing, we will estimate and plot means and confidence intervals for each group at each time point. This analysis will guide the recommendation for dose levels and evaluation times for the primary analysis in future efficacy studies.

With concerted efforts from our study coordinators and study staff we are hopeful that we can maintain excellent compliance throughout the study. In particular we expect good compliance early in the study when patients are highly motivated to feel better and return to school, work and play. However, we allow that some patients may have difficulty with compliance due to their injury, or become non-compliant once their symptoms improve. As part of this feasibility study, we will explore patterns of missing data, in particular how they may relate to the observed response (e.g. more missing data in those subjects who show better or worse processing speed) to compliance (e.g. more missing data in subjects who regularly fail to consume their supplements) and to demographics e.g. gender, age. This information will be valuable in planning future efficacy trials, and will guide our efforts to adjust for missing data. For example if the probability of missing data is associated with outcome, then non-ignorable missing data methods will be needed, whereas missing at random assumptions will be valid if the missing data can be explained by covariate information.

In addition to the primary analysis, this feasibility study will consider several approaches to modeling a smooth function for the trajectories of the individual processing speeds. The first model will fit non-linear curves to the trajectory of processing speed for the dose groups  $04/06/2018 \vee 0.16$ 

and then compare the mean curve for the BCAA dose groups to the placebo group, using an interaction term that allows differences between groups to vary over time. The basis for this model will be a smoothing spline. This first model assumes that the trajectories are smooth over time, albeit somewhat different between groups. We will carry out a hypothesis test of the difference between the groups using a likelihood ratio test for models with and without terms for the treatment effect and treatment by time interactions. A second model conceptualizes an initial increase in processing speed followed by a period of gradual improvement and by a transition where processing speed plateaus. This transition is of interest as we hypothesize that it represents the time when processing speed has returned to baseline. Here we anticipate a model using a quadratic with a change-point, with separate baseline functions for the dose and placebo groups and separate change-points. Correlation between repeated measurements on the same individual over time will be modeled using random effects i.e., a mixed effects model will also be used for these analyses.

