# 4.3.2 Total Number of Study Sites/Total Number of Subjects Projected

The study will be conducted through the Children's Hospital of Philadelphia and the Hospital of the University of Pennsylvania. Recruitment will stop when 50 subjects who are evaluable for efficacy are enrolled. A subject who is evaluable for efficacy is one who completes the study up until at least day 10 of the study. It is expected that approximately 72 subjects will be enrolled to produce 50 such subjects. All subjects who enroll and receive study medication will be evaluable for safety.

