## 7.4 Sample Size and Power

The primary analysis of the processing speed data is broadly based, reflecting the fact that that this is a feasibility study in which we have limited knowledge regarding the temporal patterns of decline and recovery in human neurocognitive functioning following concussion. We hypothesize that BCAA-treated groups will differ from placebo at specific time periods. The power calculation is based on comparisons of each dose group to placebo at each of the key time periods. These time periods each encompass three daily measurements per subject. With 10 subjects per dose group, and three repeated measurements per subject we have 80% power to detect mean differences in processing speeds between the BCAA group and the placebo group on the order of 0.122 seconds. Putting this in the context of a mean processing speed for healthy individuals of ages 14 to 34 of 2.46 to 2.51 seconds (Axon Sports unpublished), means that detectable differences between groups are on the order of 5% of the mean of a healthy individual. The analysis is based on a standard deviation in healthy individuals of 0.08, which we inflated to 0.10 based on our experience with injured or sick subjects, where variances are generally larger than their healthy counterparts. The intra-class correlation coefficient was set to 0.5. The calculation assumes a two-sided family-wise Type I error rate of 0.05 and uses a Bonferroni correction with four contrasts for each time period. The overall sample size is thus 50 subjects. We will consider a subject who contributes data up until and including at least Day 10 to be "evaluable for efficacy." We conservatively anticipate that no more than 72 subjects will be enrolled in order to achieve 50 evaluable subjects. We anticipate that it will take us approximately 12-18 months to recruit these subjects.

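### The primary analysis is called intent to treat but keeps only subjects with at least 10 days of data, and no efficacy analysis of all randomised subjects is specified

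*Combined protocol and SAP*

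**What the plan says.** Section 7.3.2 sets the primary population: "The primary intent to treat analysis will include all subjects who enroll and contribute at least 10 days of data to the study". The model is a mixed effects model tested by likelihood ratio, with Days 3-6, 7-10 and 11-14 as the key windows.

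The recruitment target uses other wording. Section 4.3.2: "A subject who is evaluable for efficacy is one who completes the study up until at least day 10 of the study". Section 7.4: "We will consider a subject who contributes data up until and including at least Day 10 to be" evaluable for efficacy, with the expectation that "no more than 72 subjects will be enrolled in order to achieve 50 evaluable subjects".

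On missing data, Section 7.3.2 accepts that "some patients may have difficulty with compliance due to their injury, or become non-compliant once their symptoms improve". It plans to explore patterns of missingness and says that if missingness is associated with outcome, "then non-ignorable missing data methods will be needed". It names no method.

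The only set of all treated subjects is for safety (Sections 4.3.2 and 7.3.4). The spline and change-point models in Section 7.3.2 and the secondary analyses in Section 7.3.3 state no population of their own.

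**The concern.** Intent to treat means that every randomised subject is analysed in the assigned arm. A minimum of 10 days of data is a condition that subjects meet or fail under treatment, so the set that remains is closer to a completer set. Randomisation no longer guarantees that the arms are comparable within it.

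Some routes to early exit can depend on arm or on outcome. Section 5.5 discontinues subjects who ask for medication for side effects. Section 10.4.2 removes those with persistent or severe gastrointestinal symptoms, or with emergent neurological or psychiatric symptoms. Section 7.3.2 itself names the injury and symptom improvement as reasons for non-compliance.

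The two definitions add a second problem: the 50 subjects who complete recruitment need not be the subjects who are analysed.

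The trial is exploratory, but the stakes go beyond it. Section 7.3.2 says of its estimates: "This analysis will guide the recommendation for dose levels and evaluation times for the primary analysis in future efficacy studies".

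**Working it through.** **1. The plan's own figure.** Inputs from Section 7.4: SD 0.10, intra-class correlation 0.5, three measurements per window, 10 subjects per arm, two-sided 0.05/4 = 0.0125, power 80%.

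- SD of a 3-day mean = 0.10 × √((1 + 2 × 0.5)/3) = 0.0816
- Detectable difference = (2.498 + 0.842) × 0.0816 × √(2/10) = 0.122 s

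The stated figure reproduces. The sample size arithmetic is not in dispute.

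**2. Planned loss.** 72 − 50 = 22, and 22/72 = 30.6%. This is a planning allowance for the Day 10 definition. It is neither an observed rate nor a figure for the 10-days-of-data set.

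**3. The definitions side by side.**

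- A subject tested only on Days 1, 4, 7 and 10 reaches Day 10 but has four days of data. This subject counts towards the 50 (if the Section 7.4 wording tolerates gaps) and falls outside the primary set.
- A subject tested on Days 0 to 9 who then leaves has 10 days of data but never reaches Day 10. This case exists only if Day 0 is a data day. The visit table in Section 5.2 lists daily assessments on Days 0-21, while Section 7.3.2 speaks of 21 time points and starts its windows at Day 1.

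To see whether the mismatch can be sized, assume that cognitive tests are the data that count, that the Day 10 test is done, and that each other test is done independently with probability 0.8. The chance of having fewer than 10 tests is:

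| Exit after | Day 0 counts | Day 0 does not count |
|---|---|---|
| Day 10 | 62% | 87% |
| Day 12 | 21% | 38% |
| Day 14 | 4% | 10% |

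For a subject who stays to Day 21 the chance is about 0.01% or less either way. The answer turns on exit day, completion rate and the status of Day 0, none of which the documents fix.

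**4. Possible bias, with no drug effect.** SD of a 4-day mean = 0.10 × √(0.5 + 0.5/4) = 0.0791. If a fraction f of an arm is lost, and loss has correlation r with processing speed, the mean of those retained shifts by r × 0.0791 × φ(z_f)/(1 − f). The ratio φ(z_f)/(1 − f) is 0.350 at f = 20%, 0.424 at 25%, 0.511 at 31%, 0.570 at 35% and 0.644 at 40%. All loss rates by arm, and r = 0.3 to 0.7, are assumptions.

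| Assumed loss | Selection | Bias (s) |
|---|---|---|
| Equal | Equal in both arms | 0 |
| 25% vs 35% | Both arms | 0.004-0.008 |
| 20% vs 40% | Both arms | 0.007-0.016 |
| 31% in each | Dose arm only | 0.012-0.028 |
| 20% placebo, 40% dose | Dose arm only | 0.015-0.036 |

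The largest value is 0.7 × 0.0791 × 0.644 = 0.036 s, which is 29% of 0.122 s.

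**5. False claims.** In a simulation of 40,000 trials (14 enrolled per arm; loss 20% on placebo, 40% in one dose arm, 31% in the others), an F-test at 0.05/3 stood in for the global test, followed by a contrast at 0.0125. That dose was falsely declared different in one window in 0.4% of trials without selection, 0.5-0.8% with selection in all arms, and 0.7-2.0% with selection in that arm only.

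**6. Effect of analysing everyone.** The mean number per arm is 72/5 = 14.4. With full data and an undiluted effect, the detectable difference is 3.340 × 0.0816 × √(2/14.4) = 0.102 s and power for 0.122 s is 0.93. If half of the 22 supply Days 3-6, n is 12.2 per arm and that window detects 0.110 s. If the average effect falls to 90%, 80% or 69% (50/72) of 0.122 s, power at 14.4 per arm with full data is 0.87, 0.76 or 0.61.

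**The case against.** The restriction stands in the same sentence as the label, so an attentive reader is not misled. The study calls itself exploratory and a feasibility study. Section 2.4 expects few side effects, Section 7.3.3 expects compliance to start falling only around Days 10 to 14, and Section 5.2 adds rewards for participation. The 72 is described as conservative. Section 7.3.2 plans to examine missingness. All three passages use the number 10 and may intend one set.

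Much of this stands. A reader might infer that about a third of subjects will be dropped and the comparison materially biased, or that false claims will multiply. The documents support neither: they give no loss by arm, every bias figure above rests on assumed values, and false rejections exceed the nominal 1.25% per contrast only towards the extreme of the one-arm case. A reader might also infer that the two definitions pick out clearly different people in known numbers. The documents do not support that either, since it depends on whether Day 0 counts, on which of the five daily assessments counts as data, and on whether Section 7.4 tolerates gaps.

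What does not stand is the view that nothing needs changing. Exploring missingness does not restore excluded subjects, an exploratory label does not make a conditioned set intent to treat, and a likelihood mixed model does not need a 10-day minimum in order to be fitted.

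**Conclusion.** The concern holds, and should be fixed. As written, the primary set is conditioned on post-randomisation behaviour, is mislabelled, and has no counterpart that includes all randomised subjects. Confidence in this is high because it rests on the text alone. The set is also worded in two ways. A subject who reaches Day 10 with missed days can count towards recruitment yet fall outside the analysis; the reverse requires Day 0 to count. The extent of that mismatch cannot be determined from the documents.

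The resulting bias is of unknown size and direction, zero to about 0.036 s under the assumptions shown and possibly near zero. Confidence in any particular value is low.

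It would be wrong to conclude that the sample size is in error, since 0.122 s reproduces, or that including everyone must raise power, since a diluted effect could lower it.

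**What to change.** - Define the primary set as all randomised subjects, in their assigned arm, with any post-baseline processing speed result. Analyse them in the planned likelihood mixed model with all data up to exit.
- Report by arm, with reasons, the subjects with no post-baseline result (still a post-randomisation condition, though a weaker one) and those with fewer than 10 days of data.
- Keep the 10-day set as a supportive analysis and do not call it intent to treat. Use one definition in Sections 4.3.2, 7.3.2 and 7.4 that says whether Day 0 counts and which assessment counts as data.
- Prespecify one missing-not-at-random sensitivity analysis, for example a range of shifts by arm for unobserved values.

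**Cost.** Revised wording and modest extra analysis; no added patients, visits or procedures. Early leavers contribute little or nothing to Days 7-10 and 11-14, and the primary result then rests on missing at random for them. If they took less study product the average effect may be diluted, so power for 0.122 s could be above or below 80%.

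**Not cured by this change.** Section 7.3.2 also says "The primary analysis will focus on results for the first 10 days of the study" while naming Days 11-14 as a primary window. That is a separate conflict to reconcile.

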# 3.1 Primary Objective

The primary objective of this study is to determine whether, compared to placebo treatment, administration of BCAA's, at one or more doses, after a concussion improves processing speed recovery at one or more time-periods post concussion. In the event that differences are observed, we will determine whether differences in processing speed between BCAA-treated and placebo-treated groups reflect differences in the maximum level of impairment and/or increases in the subsequent speed of improvement.

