## 4.4 Study Population

## 4.4.1 Inclusion Criteria

- 1) Males and females, ages 11 34 years, of any race.
- 2) Weight at least 40kg.
- 3) Subjects who had a concussion, as diagnosed by a qualified physician or advanced practice provider, within the 72 hours prior to enrollment.
- 4) Ability to have daily email and internet access.

- 5) Post-menarchal females must have a negative urine pregnancy test and must use an acceptable method of contraception including abstinence, a barrier method (diaphragm or condom), Depo-Provera, or an oral contraceptive for the duration of the study.
- 6) Subjects must, in the opinion of the referring physician, have the capacity to provide informed consent, defined by: 1) the ability to communicate; 2) the ability to assess their understanding of the treatment; 3) the ability to understand the risks and benefits of the treatment; and 4) the ability to understand the risks and benefits of not embarking on the treatment.
- 7) Informed consent by the subject, or for subjects <18 years old both informed consent by a parent/guardian and child assent.

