#### 6.1.2 Concussion History

- Concussion history will be obtained via interview: number of times diagnosed with a concussion and date of last concussion.
- History of current concussion obtained from the subject and family members, if necessary, via interview including: mechanism of injury, for sports-related concussions: sport and position and specific mechanism (head-to-head, head-to-ground, hit-to-body, etc), day and time of the injury, was the subject helmeted, presence and duration of loss of consciousness. The subject may bring a clinic note from their referring physician and refer to it for answers to these questions if they are unsure or sustained amnesia from their concussion. For CHOP patients, data may be collected directly from the medical record of their CHOP visits if subjects/parents are unable to provide.

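### The objective is set in time since concussion, but the primary model runs on day of study and the recorded time of injury enters no analysis

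*Combined protocol and SAP*

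**What the plan says.** Section 3.1 asks whether BCAA "improves processing speed recovery at one or more time-periods post concussion", and then whether any difference would "reflect differences in the maximum level of impairment and/or increases in the subsequent speed of improvement". Section 7.1 carries the same split into the hypothesis: one or more dose groups "will show a reduced nadir in cognitive performance and/or a more rapid recovery".

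Eligibility (4.4.1) requires a concussion "within the 72 hours prior to enrollment", and 10.6 sets the same 72-hour limit on starting the trial. The visit table in 5.2 makes Visit 1 study Day 0.

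The time axis of the primary analysis (7.3.2) is explicit: "We will model processing speed as a function of dose and day of study". Its windows follow that axis: "The primary analysis will consider three key time periods, Days 3-6, 7-10 and 11-14". Section 7.3.3 applies a similar approach to the other cognitive domains, posturography and sleep. The spline and change-point models in 7.3.2 refer only to time, without an origin, and the Cox model in 7.3.3 states none either.

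The concussion history (6.1.2) records "day and time of the injury". Randomisation is stratified by sex (4.2, 10.1.1). The primary model adjusts for age, and 7.3.3 adds BMI and compliance secondarily. Time since injury appears in none of these places. On the use of the results, 7.3.2 says of the estimated and plotted group means: "This analysis will guide the recommendation for dose levels and evaluation times for the primary analysis in future efficacy studies".

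**The concern.** The plan expects function to worsen and then recover along an unknown, non-linear course that begins at the injury. A subject enrolled soon after injury and one enrolled at 72 hours are at different points on that course on the same study day. Pooling them by study day mixes phases of recovery.

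Three things are affected. First, spread in lag adds between-subject variation that a recorded baseline value could remove. The reason 7.3.2 gives for adjusting for age, imbalance between dose groups, applies equally to lag. Second, the mean nadir is flattened and its apparent day moves, and the change-point, which 7.3.2 reads as return to baseline, is blurred in the same way if fitted on study day. This bears directly on the second half of the primary objective. Third, the evaluation times recommended to later trials would be stated on study day alone, without the distribution of time since injury needed to translate them.

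**Working it through.** **Inputs from the plan.** SD 0.10 s, intra-class correlation 0.5, three measurements per window, 10 subjects per group, two-sided 0.05 with Bonferroni for four contrasts, 80% power, detectable difference 0.122 s (all 7.4); enrolment 0-72 h after injury (4.4.1, 10.6).

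**Assumptions, because the plan gives no figures.** Lag from injury to Day 0 uniform on 0-3 days; change in processing speed of 0.01, 0.02 or 0.04 s per day; triangular impairment curves 0.125 s deep (5% of 2.5 s), with nadir 3-5 days after injury and recovery over 7-11 days.

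**1. The plan's own figure.**
- SD of a subject's window mean = 0.10 × √((1 + 2 × 0.5)/3) = 0.08165 s.
- SE of a two-arm contrast = 0.08165 × √(2/10) = 0.0365 s.
- Detectable difference = (2.498 + 0.842) × 0.0365 = 0.1219 s, and power at 0.122 s is 80.05%.

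The stated 0.122 s reproduces. It has no separate term for spread in time since injury.

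**2. What one window covers.** Study Days 3-6 are post-injury days 3-6 at lag 0 and days 6-9 at lag 72 h.

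**3. Chance imbalance in lag.** SD of lag = 3/√12 = 0.866 day. SE of the difference in mean lag between two arms of 10 = 0.866 × √(2/10) = 0.39 day (95% range about ±0.76 day). Multiplied by the assumed slopes, this is 0.004, 0.008 and 0.016 s, against the contrast SE of 0.0365 s.

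**4. Precision.** Add (slope × 0.866)² to 0.08165²:

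| Assumed slope (s/day) | Detectable difference (s) | Power at 0.122 s |
|---|---|---|
| 0 (as planned) | 0.1219 | 80.05% |
| 0.01 | 0.1226 | 79.5% |
| 0.02 | 0.1246 | 78.0% |
| 0.04 | 0.1325 | 71.8% |

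If the 0.10 s already contains the lag variance, adjusting for lag would instead lower the detectable difference to 0.121, 0.119 or 0.110 s.

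**5. Blurring of the mean nadir.** Averaging a triangle with rise u and recovery d over a 3-day spread of lags leaves a peak of 1 − 3/(2(u + d)) of the true depth, at study day p − 3u/(u + d), where p is the post-injury day of the nadir.

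| p, u, d (days) | Depth kept | Apparent study day |
|---|---|---|
| 3, 3, 7 | 85.0% | 2.1 |
| 4, 4, 7 | 86.4% | 2.9 |
| 5, 5, 9 | 89.3% | 3.9 |
| 3, 3, 11 | 89.3% | 2.4 |

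For the first curve, mean impairment over study Days 3-6 is 0.125 × (1 + 6/7 + 5/7 + 4/7)/4 = 0.098 s at lag 0 and 0.125 × (4/7 + 3/7 + 2/7 + 1/7)/4 = 0.045 s at lag 3 days. These are the two extremes of the enrolment window.

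**6. Nadirs already past at enrolment.** With uniform lag and nadir at day p, the share is (3 − p)/3: 67% for day 1, 33% for day 2, and none for day 3 or later. Realignment cannot recover these nadirs.

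**The case against.** The strongest defence is that study day is the right axis for comparing arms. It is time since randomisation and approximates days on treatment. Randomisation balances lag in expectation, and chance imbalance is already inside the standard error. Section 7.1 frames the expected course over the duration of the study, so the reference to time after concussion in 3.1 could be ordinary wording for follow-up. All of this stands as a reason to keep the study-day windows and tests. It does not explain leaving a recorded baseline predictor unused, or showing the trajectories only by study day.

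The size is also open to challenge. The lag distribution and curves are assumed. Enrolment near 0 h is unlikely, because diagnosis, referral and in-person screening come first (4.1.1), so 0 h against 72 h exaggerates the typical spread. At modest slopes the power loss is one or two points. That stands too.

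A reader might infer four stronger things that the documents do not support:
- **That every efficacy model uses study day.** This is explicit for the primary model and carried by reference to the longitudinal secondary endpoints. For the spline, change-point and Cox models the origin is simply not stated.
- **That the arm comparison is biased.** It is not, for the reason given above.
- **That a late enroller's first test would be taken as that subject's nadir.** The plan compares group mean curves and specifies no subject-level nadir analysis.
- **That evaluation times would be shifted by an unknowable amount.** Lag is recorded for each subject and can be reported.

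**Conclusion.** The concern holds in limited form. The objective's clock and the primary model's clock differ by 0 to 3 days between subjects, the variable that links them is collected, and no stated analysis uses it. Three further models lack a time origin. These points follow from the text alone.

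The cost to the primary test is probably small: power of 78-79.5% rather than 80% at slopes of 0.01-0.02 s/day, and 72% only at a steep 0.04 s/day. The effect on the descriptive aims is larger: a mean nadir flattened by about 11-15% and placed on a different day. Every one of these sizes rests on the assumed uniform 0-3 day lag and on the assumed slopes or curves. A narrower lag in practice would shrink them. The sample size calculation is not in dispute.

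**What to change.** 1. Keep the study-day windows and their tests.
2. Add time from injury to randomisation, from 6.1.2, as a baseline covariate (main effect) in the primary model and the longitudinal secondary models. Fit its interaction with period as a sensitivity analysis only, since 7.3.2 deliberately limits interaction terms.
3. State the time origin for the spline, change-point and Cox models.
4. Fit the spline and change-point curves, and plot the group means, on time since injury alongside the study-day versions. They should not replace them, because on the post-injury clock subjects at the same point have had up to 3 days' difference in treatment.
5. Report lag by arm.

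Do not repeat the nadir comparison without subjects whose worst score is at their first test. That selects on a post-randomisation outcome, and a treatment that prevents further worsening would produce such subjects. If a sensitivity analysis of this kind is wanted, define it by the pre-randomisation injury-to-enrolment time.

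The cost is analysis wording on data already collected. The covariate takes one model degree of freedom, and its interaction with the six periods takes five more in the sensitivity model. Data will be sparse in the first post-injury days of the realigned curves.
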